--	--

Immune Design**G100 (GLA-SE) and Pembrolizumab or Rituximab****Protocol IMDZ-G142; Version 04B; November 15, 2018**

	
An exploratory analysis will be performed on 20 efficacy evaluable relapsed or refractory FL patients and will include analyses of the frequency and duration of CRs. Efficacy evaluable patients are patients who received at least 3 injections of G100 at the recommended dose and 3 doses of rituximab, had at least one post baseline tumor assessment, and had no major protocol deviations that impact the efficacy of the study treatment or the assessment of response. Five or more CRs in 20 patients treated with G100 plus rituximab will signal an improvement of CR rate over 10%. Patients who received G100 at the recommended dose during Dose Escalation in Part 5 may be included in clinical response analysis. With 20 efficacy evaluable patients, and a historical CR rate of 10%, assuming a true CR rate of 32% in the G100 plus rituximab, this subgroup analysis has 82% power to detect a signal of an improvement in CR rate from 10% at a 1-sided alpha of 0.05.

--	--

Immune Design**G100 (GLA-SE) and Pembrolizumab or Rituximab****Protocol IMDZ-G142; Version 04B; November 15, 2018****3.2 Schedule of Events: Part 1, Dose Escalation and Part 2, Patient Expansion (G100 alone) and Large Tumor Groups**

Visit	1	2	3	4	5	6	7	8	9	10	10A	10B	11	12	Follow-up	LT Follow-up after PD	
Timeline – weeks	-4 to 0	-1	0			1	2	3	4	5	6	7	8	11	Day 112 then every 8 weeks ^h	Every 8-12 weeks	
Timeline – days	-30 to -1	-7 to -1	0	1	2	5 to 7	14	21	28	35	42	49	56	77			
Procedures																	
Informed consent / HIPAA	X																
Inclusion / exclusion criteria	X																
Demographics / Medical	X	X															
History of cancer therapy	X	X														X ^g	
Report all AEs and SAEs		X			X	X	X	X	X	X	X	X	X	X ^e			
Report possibly-related SAEs															X	X	
Record any previous / concomitant medications	X	X			X	X	X	X	X	X	X	X	X	X		X ^g	
Vital signs		X			X	X	X	X	X	X	X	X	X	X		X	
Physical exam ^a		X			X	X	X	X	X	X	X	X	X	X		X	
ECG (12-Lead)	X														X		
Tumor staging, including CT, MRI, and/or other modalities	X														X ^b	X ^b	X ^h
ECOG		X			X	X	X	X	X	X	X	X	X	X		X	
HIV, HepB, and HepC (5 mL)		X															
Beta-2-microglobulin (5 mL)	X																
Blood for phenotyping/profiling	X														X		
Blood for safety labs (10 mL)	X			X	X	X	X	X	X	X	X	X	X	X		X	
Thyroid function tests ^f (5 mL)	X																
Blood for T cell gene profiling	X														X		
Urinalysis	X																
Pregnancy test ^c		X													X		
Local Radiation 2Gy qd x2				X	X												

Immune Design**G100 (GLA-SE) and Pembrolizumab or Rituximab****Protocol IMDZ-G142; Version 04B, November 15, 2018**

Visit	1	2	3	4	5	6	7	8	9	10	10A	10B	11	12	Follow-up	LT Follow-up after PD
Timeline – weeks	-4 to 0	-1	0			1	2	3	4	5	6	7	8	11	Day 112 then every 8 weeks ^h	
Timeline – days	-30 to -1	-7 to -1	0	1	2	5 to 7	14	21	28	35	42	49	56	77	Day 112 then every 8 weeks ^h	Every 8-12 weeks
Procedures																
G100 dosing					X	X	X	X	X	X	X	X	X			
Tumor biopsy	X												X ^d	X ^d		
Clinical Status, treatment history																X ^g
Blood volume per visit (mL)		38	0	0	10	10	10	10	23	10	10	23	10	10		
Total blood volume		38	38	38	48	58	68	78	88	111	121	131	154	164	174	

^a Physical exam also includes tumor measurements of treated and any untreated lesions measurable by exam. If appropriate, photographs should be taken to document lesions.

^b Day 56 restaging CT or MRI scans should be performed if the optional treatment #9 is not given. If a PET CT is used, a standard high resolution CT series should be obtained rather than low resolution scans for tumor measurements. However, PET scans should not be used to determine disease progression since it is expected that PET avidity will increase with the type of inflammation induced by this treatment and may lead to false positive results. Confirmation of disease progression by CT or MRI must be performed 4 or more weeks later per IrRC. If the 9th dose is given, then CT/MRI should be delayed to Day 63 to 77. Photographs: if the tumor can be measured and assessed visually, photographic documentation with measurements should be considered in order to keep a record and help assess any response to treatment (may be performed at any time during study)

^c Pregnancy test should only be performed on FCBP. Urine pregnancy test is recommended and must be performed (and negative) within 7 days prior to starting study treatment and on day 77. Site may use serum pregnancy test if part of their procedures. For patients in the UK and France, urine pregnancy tests must also be performed every month or sooner while the patient is receiving G100.

^d Post-treatment biopsy should be done on Day 56 +/- 7 days for patients not receiving optional treatment #9. If the 9th dose is given, biopsy should be delayed to Day 63 to 77.

^e Patients should have all AEs reported for at least 30 days following the last dose of the G100 study agent. This includes those who withdraw early before completion of the study.

^f Thyroid function tests (including TSH) should be performed at screening in those patients being evaluated to participate and be randomized in Part 2 G100 vs. G100 plus pembrolizumab.

^g Patients will receive telephone follow-up or clinic visit every 8 to 12 weeks after disease progression until 1 year after first study injection. Follow-up will include vital status (survival), cancer status (e.g., lymphoma transformation), and post-treatment anti-cancer therapy including time to next treatment, treatment details, and clinical response. If the patient agrees, the site may periodically (e.g. every 2 to 4 months) contact the patient beyond 1 year to check on vital and cancer status.

^h Imaging studies during Follow-up will occur on Day 112, every 8 weeks thereafter for the first year, every 3 to 4 months for the second year, and then at least every 6 months for the third and subsequent years.

Immune Design

G100 (GLA-SE) and Pembrolizumab or Rituximab

Protocol IMDZ-G142; Version 04B; November 15, 2018

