	
immune cells within the tumor microenvironment, including T cells, NK cells, macrophage and dendritic cells. Rituximab can potentially increase the loading/pulsing of dendritic cells with tumor antigen, leading to more effective antigen presentation of rare tumor antigens. Rituximab and other similar antibodies that bind to tumor cells and debris have been previously shown to facilitate the uptake and processing of tumor antigens by dendritic cells through opsonization/phagocytosis. In addition, a known mechanism of action of rituximab is through antibody dependent cellular cytotoxicity (ADCC). In preclinical work, the combination of G100 with rituximab demonstrated enhanced ADCC. Therefore, G100 in combination with rituximab can increase the amount of tumor antigen processed by dendritic cells potentially leading to greater T cell stimulation/activity; in addition, the combination could enhance tumor cytotoxicity by activating and increasing the number of ADCC effector cells.
 
In this study, a Dose Escalation will be performed first followed by Patient Expansion. During Dose Escalation 12-24 patients and during Patient Expansion 20 evaluable patients as defined in the Statistical Section will be enrolled. Patient enrollment will be monitored. Patients who received G100 during Dose Escalation in Part 5 may be included in clinical response analysis.
 
Data from the G142 study indicate that the G100 intratumoral dose of 20μg is relatively safe with only grade 1 or 2 related AEs reported and no DLTs and that this higher dose appears to induce greater numbers of infiltrating CD8 T cells into the tumor. Recent preclinical data indicate that G100 doses greater than 20 μg can lead to improved survival of animals in tumor models, further supporting that additional dose exploration may be warranted. Therefore, this arm will examine escalating doses of G100 plus rituximab in a single tumor site utilizing a 3+3 design in order to establish safety and examine clinical and biomarker responses. Once the highest safe dose/systemic exposure is determined from the Dose Escalation portion of the study, all safety, efficacy and biomarker data will be reviewed by the Sponsor (in collaboration with the independent DMC) and either the highest dose determined to be safe or the most biologically active and safe dose (if different than the MTD) will be chosen for further investigation. A Patient Expansion group would then begin. Details of Dose Escalation and Patient Expansion are described below.
 
Part 5, Dose Escalation
 
In the Dose Escalation portion, safety and efficacy of G100 injected into a single tumor lesion without radiation will be assessed using a 3+3 design where patients will be assigned to sequential cohorts of escalating doses of intratumoral G100 in combination with standard dose induction therapy with rituximab (Figure 8 and Figure 9). Treatment will begin on Day 0 with rituximab 375mg/m² IV and continue weekly for a total of 4 doses. If there are no DLTs or significant safety events after the first dose of rituximab, G100 will be injected intratumorally beginning on Day 1, and then dosing

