--	--

Immune Design**G100 (GLA-SE) and Pembrolizumab or Rituximab****Protocol IMDZ-G142; Version 04B; November 15, 2018**

	
During Part 2 and based on the continuous review of safety events, if the dose of 10 µg G100 is used during Patient Expansion and subsequently determined to have an increased safety risk, the DMC may recommend and the Sponsor may choose to reduce the dose of G100 to 5 µg or they may recommend stopping the G100 treatment. If the 5 µg dose level is determined not to be safe by the independent DMC, treatment with G100 will be stopped. Following evaluation by the DMC and the Sponsor, a further modification to the dose/treatment schedule could be recommended.
 
During Part 4 and based on the continuous review of safety events, if the dose of 20 µg/lesion G100 plus pembrolizumab is subsequently determined to have an increased safety risk, the DMC may recommend and the Sponsor may choose to reduce the dose of G100 to 10µg or they may recommend stopping the G100 treatment.
 
Similarly during Part 5, if G100 plus rituximab is subsequently determined to have an increased safety risk, the DMC may recommend and the Sponsor may choose to reduce the dose of G100 or they may recommend stopping the G100 treatment. As described in the Part 5 design, an optional cohort may be examined where the dose level associated with a DLT is split in two lesions in order to help determine if the lack of tolerability of the dose was due to the treatment of a single lesion or was limited due to the total systemic G100 exposure. Following evaluation by the DMC and the Sponsor, a further modification to the dose/treatment schedule could be recommended.
 
All patients treated with one or more injections of G100 will be considered part of the safety data set. Patients will be followed every 8 weeks until disease progression as defined by the irRC. Patients with disease progression by irRC (or symptomatic deterioration) will be followed thereafter every 8-12 weeks by telephone or clinical visit for up to one year (or longer if the patient agrees) after first study injection as long as they are able to engage in follow-up. Follow-up will ascertain vital status (survival status) as well as cancer status (e.g., lymphoma transformation), post-treatment anti-cancer therapy (including time to next treatment, treatment details, and clinical response), and any SAE that might be possibly related to G100 treatment. Patients followed on this study have developed delayed objective tumor responses occurring >18 months from study start. If patients develop late responses after initial IrRC progression but have not received additional therapy, they may be asked to consent to additional follow-up of clinical response and biomarker analyses.

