6.2 Dose-Limiting Toxicities

DLTs will be used to establish safety parameters for stopping dose escalation and will follow a standard 3+3 study design. AE severity assessments will be performed using National Cancer Institute (NCI) Common Terminology Criteria for Adverse Events (CTCAE) v4.03 or newer. Unacceptable toxicity is defined when two or more subjects in a dose level cohort develop DLTs

considered at least possibly related to the study regimen. Further dosing at that level will be discontinued. Hospitalizations primarily intended to expedite diagnostic evaluations or for elective surgery will not be considered as SAEs for the purpose of ascertaining DLT. The occurrence of any of the following toxicities during the first 28 days will be considered a DLT, if assessed by the investigator to be possibly, probably, or definitely related to any component of study treatment (G100, pembrolizumab, or rituximab).

1. Grade 4 nonhematologic toxicity (not laboratory)
2. Grade 4 hematologic toxicity lasting \geq 7 days, except thrombocytopenia:
 - Grade 4 thrombocytopenia of any duration
 - Grade 3 thrombocytopenia associated with clinically significant bleeding
3. Any nonhematologic AE \geq Grade 3 in severity should be considered a DLT, with the following exceptions: Grade 3 fatigue lasting \leq 3 days; Grade 3 diarrhea, nausea, or vomiting without use of anti-emetics or anti-diarrheals per standard of care; Grade 3 rash without use of corticosteroids or anti-inflammatory agents per standard of care.
4. Any Grade 3 or Grade 4 nonhematologic laboratory value if:
 - Clinically significant medical intervention is required to treat the subject, or
 - The abnormality leads to hospitalization, or
 - The abnormality persists for >1 week.
 - The abnormality results in a Drug induced Liver Injury (DILI)
 - Exceptions: Clinically nonsignificant, treatable, or reversible laboratory abnormalities including liver function tests, uric acid, etc.
5. Febrile neutropenia Grade 3 or Grade 4:
 - Grade 3 is defined as ANC $<1000/\text{mm}^3$ with a single temperature of >38.3 degrees C (101 degrees F) or a sustained temperature of ≥38 degrees C (100.4 degrees F) for more than 1 hour
 - Grade 4 is defined as ANC $<1000/\text{mm}^3$ with a single temperature of >38.3 degrees C (101 degrees F) or a sustained temperature of ≥38 degrees C (100.4 degrees F) for more than 1 hour, with life-threatening consequences and urgent intervention indicated.

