12.0 ADVERSE EVENTS

All patients who receive at least one study injection or another study-related procedure will be considered evaluable for safety parameters. This includes any untoward signs (including abnormal laboratory findings) or symptoms experienced by the patient from the time of enrollment until the EOS / Post Vaccination Safety Visit (i.e., last study visit before long-term follow-up). For patients enrolled on the pembrolizumab arm, all AEs experienced from the time of enrollment through 30 days following cessation of treatment will be reported by the investigator. Safety will be evaluated for all treated patients using the *NCI CTCAE v.4.03* or newer. Safety assessments will be based on medical review of both solicited and spontaneously reported AEs, including symptoms, physical examination findings, vital signs, laboratory findings, ECGs, and discontinuations for AEs. The nature, severity, and frequency of AEs will be monitored on an ongoing basis for risk assessment and to determine if risk management interventions are warranted (i.e., expedited notification of safety findings to investigators, IRBs or regulators; update of IB and ICF risks and re-consenting study patients; revision of safety monitoring procedures; revision of eligibility criteria or other study procedures; etc.).

Progression of the cancer under study is not considered an AE unless it is considered to be drug-related by the investigator.

All SAEs that are unexpected and considered possibly, probably or definitely related to study regimen will be reported to the FDA and IRB in accordance with the requirements in 21 code of federal regulations (CFR) §312.32.

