14.3 Definition and Analysis of Primary and Secondary Endpoints

14.3.1 Safety

All enrolled patients who receive at least one injection of study drug or undergo a study-related procedure will be included in the safety analysis. The highest toxicity grades per patient will be tabulated for AEs and laboratory measurements, and the number and percent of patients reporting AEs will be quantified. Listings will be required for all on-study deaths, SAEs, DLT, and AEs that lead to withdrawal from study. Narratives for all SAEs and deaths on-study will be required.

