### **4.2 Safety Population**

The Safety Population includes all enrolled patients who received at least one injection of G100 after standard local radiation. Safety data analyses will be conducted on all patients in the Safety Population according to the treatment received.

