## **5.7 Safety Evaluation**

Safety evaluation will be based on safety population.

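### SAP 4.2 makes a G100 injection a condition of the Safety Population, so a Part 5 patient kept from G100 by a Day 0 rituximab event is missing from the safety summary tables, contrary to Protocol 12.0 and 14.3.1

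*Protocol*

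**What the plan says.** The documents contain two rules for who belongs in the safety analysis.

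- **G100 rule.** The synopsis (Safety Monitoring) and the closing part of Section 4.7 say: "All patients treated with one or more injections of G100 will be considered part of the safety data set". Section 4.7 also states it in its Part 1 paragraph, there in terms of G100 doses. SAP 4.2 adopts it with a further condition: "The Safety Population includes all enrolled patients who received at least one injection of G100 after standard local radiation". SAP 5.7 then says: "Safety evaluation will be based on safety population".
- **Wider rule.** Protocol 12.0 says: "All patients who receive at least one study injection or another study-related procedure will be considered evaluable for safety parameters". Protocol 14.3.1, the protocol's own statistical section, says: "All enrolled patients who receive at least one injection of study drug or undergo a study-related procedure will be included in the safety analysis".

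SAP Section 9, which lists changes to the planned analysis, mentions only the Lugano assessment and the independent radiology review.

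For Part 5, the synopsis and Section 6.1 make G100 conditional on the first rituximab infusion: "If there are no DLTs or significant safety events after the first dose of rituximab, G100 will be injected intratumorally beginning on Day 1". Protocol 6.2 counts an event as a DLT if it is judged possibly, probably or definitely "related to any component of study treatment (G100, pembrolizumab, or rituximab)".

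**The concern.** The nature, frequency and severity of adverse events under rituximab plus G100 are part of the Part 5 primary endpoint. Study treatment in Part 5 starts with rituximab, and it is toxicity that can keep a patient from G100. A safety set defined by G100 injection therefore leaves out patients because of the outcome being measured. Protocol 8.1.8.4 foresees the mechanism: it notes that severe rituximab reactions are typically seen with the first infusion.

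The SAP is also at odds with itself. Its definition of a treatment-emergent event (SAP 5.7.2) runs from the start of study treatment, not from the first G100 dose. A Day 0 rituximab reaction is thus a treatment-emergent event, possibly in a patient who is outside the population being tabulated.

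At stake are the summary incidences and denominators in the study report. In cohorts of 3 to 6 patients, one exclusion changes the picture.

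**Working it through.** The plan gives no figure to reproduce on this point. The check compares the definitions and then sizes the effect.

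**1. One patient under each rule.** Take a Part 5 patient who receives rituximab on Day 0, has a rituximab-related DLT, and never receives G100.

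| Source | Condition | Patient included? |
|---|---|---|
| Protocol 12.0 | study injection or study-related procedure | yes |
| Protocol 14.3.1 | study-drug injection or study-related procedure | yes |
| Protocol 6.1, cohort advancement | DLT during the safety period suffices | yes, and not replaced |
| SAP 4.2 | at least one G100 injection | no |
| SAP 5.7 summary tables, including DLTs | Safety Population | no |

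It can be argued whether an intravenous infusion is an injection of study drug under 14.3.1. The study-procedure clause covers the patient either way.

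Moving G100 to Day 0 in Patient Expansion would not close the gap. Under the note in Protocol 10.3.24, G100 would still follow rituximab that day.

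**2. Effect on a cohort's DLT table.** Each excluded patient with a DLT leaves both the numerator and the denominator.

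- 1 DLT in 6, that patient never injected: 1/6 = 16.7% becomes 0/5 = 0%.
- 1 DLT in 3, that patient never injected: 1/3 = 33.3% becomes 0/2 = 0%.
- 2 DLTs in 6, one of the two patients never injected: 2/6 = 33.3% becomes 1/5 = 20.0%. A cohort that fails the less-than-one-third criterion would be tabulated as if it met it.

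**3. How likely an exclusion is.** Part 5 plans 12-24 patients in escalation and 20 efficacy evaluable patients in expansion, so N is roughly 32 to 44. The documents give no rate q for Day 0 events that permanently prevent G100, so q is assumed. The expected number excluded is qN, and the chance of at least one is 1 − (1 − q)^N.

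| Assumed q | Expected, N = 32 | Chance of ≥1, N = 32 | Expected, N = 44 | Chance of ≥1, N = 44 |
|---|---|---|---|---|
| 1% | 0.32 | 27.5% | 0.44 | 35.7% |
| 3% | 0.96 | 62.3% | 1.32 | 73.8% |
| 5% | 1.6 | 80.6% | 2.2 | 89.5% |
| 10% | 3.2 | 96.6% | 4.4 | 99.0% |

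Within a single cohort of 6, the chance of at least one exclusion is 5.9% at q = 1% and 46.9% at q = 10%.

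**4. Parts 1 to 3.** A patient irradiated on Days 0 and 1 but never injected falls outside SAP 4.2 in the same way. The documents suggest no toxicity mechanism there, so this is a matter of completeness rather than bias.

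**The case against.** Several points on the other side are sound and limit the reach of the concern.

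- **The protocol sentence is not exclusive.** A reader might infer that the synopsis and Section 4.7 bar patients who had no G100. They say that injected patients belong to the set, not that only they do, and can stand beside 12.0 and 14.3.1. The definite conflict is between SAP 4.2 and those two sections.
- **Safety decisions are protected.** A reader might infer that a DLT could be lost to escalation or monitoring. It would not be. A patient with a DLT stays evaluable for cohort advancement (6.1), and the DMC reviews DLTs and possibly related SAEs as they are reported (4.7). SAP 5.7.2 lists all adverse events, and 14.3.1 requires narratives for SAEs and deaths.
- **A hold on Day 1 need not be permanent.** Dosing visits have a window of ±2 days and only delays beyond 14 days are barred (10.1). G100 after a DLT may be considered case by case (6.5). Only patients who never receive G100 are affected.
- **The extreme example is rare.** A cohort closed after 2 Day 0 DLTs in 3 patients would be shown as 0 of 1. Even if every Day 0 event were a DLT, the chance of two or more in three patients is 3q²(1 − q) + q³, which is 0.12%, 0.7% or 2.8% at q = 2%, 5% or 10%.
- **Not every rate is biased downward.** The Day 0 events themselves are undercounted. For later events, and for G100-related events, adding never-injected patients enlarges the denominator and lowers the rate.
- **Practical reach is uncertain.** SAP Section 9 records that the sponsor terminated the study. The SAP version log still covers cohort 5, but the documents do not say how many Part 5 patients were treated.

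None of this reconciles SAP 4.2 with 14.3.1. Listings and narratives do not replace an incidence with the correct denominator for a primary endpoint.

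**Conclusion.** The concern holds as an undeclared conflict over the analysis set. The SAP's Safety Population is narrower than the one in Protocol 12.0 and 14.3.1, and in Part 5 the patients it omits can be selected by toxicity. The resulting error lies in the summary AE, SAE, death and DLT incidences and their denominators.

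The number of patients is likely to be small: an expected 0.3 to 4.4 over the assumed rates of 1-10% and N of 32-44, with a 28-99% chance of at least one. Those rates are assumptions without a source in the documents. N is approximate too: fewer than four cohorts may be run, escalation patients at the recommended dose may count in the response analysis, and the 20 in expansion are efficacy evaluable patients rather than all treated.

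This should be corrected before the safety tables are produced. Safety is analysed descriptively without a hypothesis test, and the affected patients remain visible elsewhere, so it does not undermine the conduct of the trial.

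**What to change.** 1. In SAP 4.2, define the Safety Population as all enrolled patients who received any dose of any study treatment: G100, pembrolizumab, rituximab or, in Parts 1-3, protocol radiation. Drop the prior-radiation condition for Parts 4 and 5. Those parts omit radiation (Protocol 8.3), so read literally that condition excludes all their patients.
2. Use the same definition in the synopsis, in both places in Section 4.7, and in Sections 12.0 and 14.3.1. The last two need the edit as well, because they also admit patients who had only a study procedure, such as a screening biopsy. Leaving them would keep two rules in force.
3. SAP 4.2 analyses safety by treatment received, so state that never-injected patients are shown under their assigned part and cohort.
4. Keep the G100-injected subset as the denominator for the G100-related AE tables.

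The cost is a few sentences in each document and no new data. Some reported rates may be slightly less favourable. The supportive efficacy analysis, which SAP 5.6 runs on the Safety Population, would also gain these patients in its denominator.
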